#### Secondary outcome

Secondary outcome measures will include:

- I. ROC curve of stool FIT plus urine VOC in detection of SBD.
- II. The potential number of colonoscopies and CTCs avoided in those without SBD,
- III. Total NHS & Personal Social Services (PSS) costs, and
- IV. Total quality-adjusted life years (QALYs) associated with each option.

Exploratory outcome measures will include:

Calculation of the number of CTC negative participants who later present with SBD or microscopic colitis

IRAS 282247\_RECEDE protocol\_v2.2\_11.02.2022 Page **13** of **50** 

 Sensitivity, specificity, NPV and PPV of stool FIT plus urine VOC in the detection of SBD + microscopic colitis

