#### Economics

- Estimation of per-participant NHS & Personal Social Services (PSS) costs associated with each of the compared options (FIT plus urine VOC compared to FIT alone, as indicators for colonoscopy)
- Impact of colonoscopy and CTC on participants' health-related quality of life (colonoscopy disutility including bowel preparation).
- Number of potentially avoidable colonoscopies, CTCs and resulting savings. We will also consider opportunity benefits such as reduced waiting times for other participants
- Estimation of quality-adjusted life years (QALYs) associated with each of the compared options (FIT plus urine VOC compared to FIT alone)
- Overall cost-effectiveness of adding VOC testing in the diagnostic pathway.

All 1,915 participants clinical data and surplus samples associated metadata will be stored in the Arden Tissue Bank (hosted at UHCW) and will be made available (upon written application and approval by the TSC and Chief Investigator) for Universities, NHS and commercial researchers worldwide for further research.

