8.3 Economic evaluation

An economic analysis will be carried out to determine the costs, benefits and overall cost-effectiveness of FIT + VOC versus FIT followed by colonoscopy or CTC in participants with gastrointestinal symptoms referred for investigation.

As recommended, and in order to meet the needs of NICE for a future technology appraisal, the analysis will be carried out principally from the perspective of the NHS and Personal Social Services (PSS) and it will employ a decision analytic model built as part of this study. Should relevant data be available, additional analyses will consider wider costs that are likely to differ between the compared options, including productivity loss resulting from time taken off paid employment (40, 41).

A review of the literature will be carried out to identify existing decision models used in the broader clinical area, insights from which will inform the structure of a de novo decision model tailored to address the particular decision problem. A preliminary review of the literature has identified only a few relevant decision models, the key one being the model developed as part of NICE Guidance on recognition and referral of suspected cancers (NICE Guideline NG12) (42). This work has informed two more recent models investigating the cost-effectiveness of FIT test as a diagnostic aid for colorectal cancer referrals in primary care commissioned by NICE  and the NIHR Health Technology Assessment programme (7). All of these models have employed a multi-part structure, and at this stage, it is envisaged that our model will follow a similar structure, as this is suitable for delineating and capturing short and long-term costs and consequences (accruing over a lifetime horizon). In particular, it is possible that the model will consist of the following three parts:

- (i) a decision tree delineating and modelling the short-term cost and consequences (life years and QALYs) resulting from the possible findings (diagnoses) following the use of each diagnostic option
- (ii) a simple state-transition model capturing the long-term costs and consequences accruing over a life-time horizon, associated with the treatment and progression of SBD, and
- (iii) a simple state-transition model reflecting long-term costs and consequences in participants without SBD.

IRAS 282247\_RECEDE protocol\_v2.2\_11.02.2022 Page 29 of 50

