IRAS 282247\_RECEDE protocol\_v2.2\_11.02.2022 Page **30** of **50** 

EQ-5D is a widely used generic measure of health-related quality of life that enables the calculation of QALYs and is recommended for use in economic evaluations in health care (47,48). The descriptive part of the EQ-5D-5L questionnaire (which comprises questions on mobility, self-care, usual activities, pain/discomfort, anxiety/depression) and the accompanying visual analogue scale ask participants about their quality of life on the particular day and will be administered at (i) baseline (i.e. when participant consent is received) (ii) immediately prior to colonoscopy or CTC once the participant has fully completed bowel preparation, (iii) 24 hours after the colonoscopy or CTC examination, (iv) 72 hours post colonoscopy or CTC and (v) 3 weeks post colonoscopy or CTC. Collected data from the EQ-5D-5L (5-digit numbers describing the respondent's health state at different points in time) will be subsequently translated into preference-based health related quality of life indices using available value sets (49, 50).

In line with recommendations, final results will be presented in terms of total costs (discounted at 3.5% per annum) per additional QALY associated with each of the compared options (51). Deterministic and probabilistic sensitivity analyses will be undertaken to explore the robustness of the obtained results to sample variability and plausible variations in key assumptions and employed analytical methods . The model will also form the basis for conducting value of information analysis, which will quantify the total expected cost due to the remaining uncertainty around the decision problem (53, 54).

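### Section 8.3 defines the economic result as total, not incremental, cost per additional QALY, which does not answer the question of adding VOC

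*Protocol*

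**What the plan says.** Section 8.3 closes by fixing how the economic result will be reported: "final results will be presented in terms of total costs (discounted at 3.5% per annum) per additional QALY associated with each of the compared options". It presents this as following recommendations and cites the NICE methods guide.

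Other parts of the protocol set the question as a comparison:

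- Section 2.1, Economics, lists as an objective "Overall cost-effectiveness of adding VOC testing in the diagnostic pathway".
- Section 8.3 opens by promising the "costs, benefits and overall cost-effectiveness of FIT + VOC versus FIT followed by colonoscopy or CTC".
- The secondary outcomes in section 1.2 include "Total NHS & Personal Social Services (PSS) costs, and" and "Total quality-adjusted life years (QALYs) associated with each option".
- The model is to run over a lifetime, with one part "capturing the long-term costs and consequences accruing over a life-time horizon".
- The evaluation is designed "in order to meet the needs of NICE for a future technology appraisal".

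Section 8.3 nowhere mentions an incremental cost, an incremental cost-effectiveness ratio or a net benefit, and it gives no discount rate for QALYs.

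**The concern.** The numerator is absolute and the denominator is incremental. Most of the cost of FIT + VOC would also be incurred under FIT alone, because FIT-positive participants are referred and diagnosed disease is treated under either option. Charging that shared cost to the extra QALYs does not measure what adding VOC buys.

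The sentence also promises the figure for each option. FIT alone, as the comparator, has no additional QALY, so no ratio exists for it.

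This is the headline of an evaluation meant for NICE. If the sentence is followed, the published figure misstates the value of adding VOC. If it is not followed, the analysts depart from a pre-specified rule without a record of why.

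**Working it through.** The protocol reports no cost-effectiveness figure, so there is nothing to reproduce. The check is algebra, followed by two illustrations of size.

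**Algebra.** Let A be FIT alone and B be FIT + VOC, with mean costs C and mean QALYs Q.

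- As written, for B: R = C_B / (Q_B − Q_A).
- Needed for the stated question: ICER = (C_B − C_A) / (Q_B − Q_A).
- Hence R / ICER = C_B / (C_B − C_A). The QALY gain cancels.

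Three consequences follow:

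1. If B costs more than A, the factor exceeds 1 and R overstates the cost per QALY gained.
2. If B costs less and gains QALYs, B dominates, yet R is still positive and the saving is hidden.
3. For A, the denominator is Q_A − Q_A = 0 and R is undefined.

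A cost K common to both options leaves C_B − C_A unchanged but raises the numerator, so the factor becomes (C_B + K)/(C_B − C_A). Shared treatment costs therefore always widen the gap when B costs more.

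**Illustration 1: diagnostic costs only.** Inputs from the protocol:

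- FIT costs £18 and VOC £25 (section 1.9).
- In the two-week-wait study in Appendix E, 135 of 612 were FIT positive (0.2206). The 477 FIT negatives included 5 cancers, which is 95.4 colonoscopies saved per cancer missed, valued at almost £70,000. That gives about £70,000/95.4 = £734 per colonoscopy.
- Assumption: 400 to 600 of every 1,000 are negative on both tests. This borrows the Figure 6 scenarios, which the protocol does not offer as an expected rate.

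FIT alone: 18 + 0.2206 × 734 = £180.

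Serial FIT + VOC: 18 + 0.779 × 25 + (proportion referred) × 734.

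| Proportion referred | FIT + VOC | Difference from £180 | Total / difference |
|---|---|---|---|
| 0.6 | £478 | £298 | 1.60 |
| 0.5 | £404 | £225 | 1.80 |
| 0.4 | £331 | £151 | 2.19 |

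**Illustration 2: assumed whole-pathway costs.** Every input here is an assumption, except that +£25 is the price of the VOC test. The QALY gain is set at 0.01.

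| FIT-alone total | Cost difference | ICER | Ratio as written | Factor |
|---|---|---|---|---|
| £500 | +£100 | £10,000 | £60,000 | 6 |
| £500 | +£25 | £2,500 | £52,500 | 21 |
| £5,000 | +£100 | £10,000 | £510,000 | 51 |
| £5,000 | +£25 | £2,500 | £502,500 | 201 |
| £5,000 | −£100 | dominant | £490,000 | sign lost |

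The spread from 1.6 to 201 shows that the assumptions drive the size. The direction, for any positive cost difference, does not depend on them.

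**The case against.** The best defence is that this is a drafting slip. Sections 2.1 and 8.3 frame the evaluation as FIT + VOC against FIT, and section 1.2 lists total costs and total QALYs as outcomes, so the right ratio is one subtraction away. The word total may mean all NHS and Personal Social Services cost categories rather than cost before subtraction. This is probably what happened, and it limits the seriousness. It does not remove the fault: section 8.3 states the result measure outright, defers it to no other document, and no other sentence in the protocol gives the incremental ratio.

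The magnitudes are open to fair criticism. The colonoscopy cost is back-calculated from a rounded figure. The FIT-positive rate comes from two-week-wait referrals, whereas RECEDE also recruits routine ones. The Figure 6 counts are precision scenarios for NPV. These criticisms stand, and the factors should be read as illustrations only. Overstatement is also not universal: if VOC saves money, the fault is a lost sign. On diagnostic cost at the fixed FIT threshold a saving is not expected, because the either-positive rule refers every FIT-positive participant and some others, so it would have to come from later treatment costs or revised thresholds.

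A reader might infer that QALYs will be left undiscounted, since the 3.5% is attached to costs. The protocol does not say so. It is silent on the QALY rate, points to the NICE methods guide, and may leave the detail to an analysis plan not shown.

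**Conclusion.** The sentence is wrong as written. It pairs total cost with additional QALYs, so it does not measure the cost-effectiveness of adding VOC, it cannot show dominance, and it has no value for the FIT-alone comparator. That conclusion needs only algebra and the protocol's own statement of its question. The size cannot be fixed from the protocol: about 1.6 to 2.2 times on illustrative diagnostic costs, and larger with shared treatment costs.

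It would go too far to say that the ratio is wrong for every strategy. For the comparator it is undefined, and no computed ratio exists to be shown wrong. Nor do the documents show that the figure would cross a decision threshold, because they give neither a threshold nor an expected QALY gain.

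On discounting, the finding is only that the rate for QALYs should be stated. The lifetime horizon is why it matters: if QALYs were in fact undiscounted, a level yearly gain would be overstated by a factor T / Σ 1.035^(−t), with t from 0 to T − 1. That is 10/8.61 = 1.16 at 10 years and 40/22.10 = 1.81 at 40 years.

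This is a minor correction to a secondary economic outcome. Sample size, data collection, model structure and the primary accuracy analysis are untouched.

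**What to change.** Replace the sentence in section 8.3 with wording such as:

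> Results will be presented as the incremental cost per additional QALY of FIT + VOC versus FIT (difference in mean discounted costs divided by difference in mean discounted QALYs, with dominance reported where it occurs). Total costs and total QALYs will be tabulated for each option. Costs and QALYs will both be discounted at 3.5% per annum.

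The same definition should be carried into any health economics analysis plan. The cost is one sentence, with no change to data, conduct or model. If the team intends a different discount rate for QALYs, it should state that rate and the reason in the same place.

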#### \*non-voting members

The role of the Trial Steering Committee (TSC) will be to provide overall supervision of the study, in particular with respect to the progress of the study, adherence to the protocol, participant safety and the review of new information. The TSC has reviewed and agreed the final version of the protocol. Meetings will be held at regular intervals determined by need, but no less than twice a year or at times determined by stages such as recruitment targets. A TSC Charter will be agreed at the first meeting which will detail how it will conduct its business.

#### 9.1.2 Study Co-ordinator/Manager

The Study Co-ordinator/Manager will have responsibility for overseeing day to day coordination of the study and reporting regularly to the TSC. The Study Manager's responsibilities include, but are not limited to:

- Coordinating protocol development, participant and study management documents;
- Correspondence with study funder and tracking of progress against agreed milestones;
- Setting up and maintaining the Study Master File;
- Ensuring necessary approvals are in place before the start of the study at each site;
- Providing training to study personnel;
- Providing data management support; including data input, maintenance of the study database and raising of queries;
- Producing study progress reports, in particular recruitment against targets, and coordinating TSC meetings and minutes;
- Ensuring data security and quality and ensuring data protection laws are adhered to;
- Ensuring complete records are in place for audit and monitoring purposes;
- Ensuring the study is conducted in accordance with the ICH GCP;
- Archiving all original study documents including the data forms in line with UHCW NHS Trust policy; and
- Visiting study centres and liaison with centre PIs and other staff.

#### 9.1.3 Principal Investigators

Site Principal Investigator responsibilities include, but are not limited to:

- Ensuring that the study is conducted as set out in the protocol and supporting documents;
- Delegating study related responsibilities only to suitably trained and qualified personnel and ensuring that those with delegated responsibilities fully understand and agree to the duties being delegated to them;
- Ensuring that CVs and evidence of appropriate training for all Site staff are available in the Study Site File;
- Ensuring that all delegated duties are captured in the study Delegation Log;
- Ensuring all Adverse Events (that are specifically as a result of study-related activity) are documented and reported promptly to the Study Manager;
- Accountability for study treatments at their site;
- Ensuring the study is conducted in accordance with ICH GCP principles;
- Allowing access to source data for monitoring, audit and inspection; and
- Ensuring that all source data is complete and provided to the Study Manager at regular intervals.

IRAS 282247\_RECEDE protocol\_v2.2\_11.02.2022 Page **32** of **50** 

#### 10 MONITORING, AUDIT & INSPECTION

The study may be monitored by the Research & Development Department at UHCW as representatives of the Sponsor, to ensure that the study is being conducted as per protocol, adhering to Research Governance and GCP. The approach to, and extent of, monitoring may be specified in a study monitoring plan determined by the risk assessment undertaken prior to the start of the study.

#### **11 ETHICAL AND REGULATORY CONSIDERATIONS**

#### 11.1 Ethical approval and research governance

The study will be conducted in compliance with the principles of the ICH GCP guidelines and in accordance with all applicable regulatory guidance, including, but not limited to, the UK policy framework for health and social care research. Ethical approval for this study will be sought from the Research Ethics Committee combined with Health Research Authority (HRA) approval. No study activities will commence until favourable ethical opinion and HRA approval has been obtained. Progress reports and a final report at the conclusion of the study will be submitted to the approving REC within the timelines defined by the committee. Confirmation of capacity and capability will be obtained from the R&D department prior to commencement of the study at all participating sites.

#### 11.2 Peer review

RECEDE study has been peer reviewed by the NIHR HSD&R grant awards committee. This protocol has also been reviewed externally by the Trial Steering Committee and internally by the Trial Management Group.

#### 11.3 Public and Participant Involvement

RECEDE study was reviewed by members of the GUT club (survivors of gastrointestinal related cancer) and UHCW participant research advisory group at outline stage and again at Stage 2 of the application. The main theme from these consultations were support for non-invasive tests to diagnose SBD and thereby avoid need for a colonoscopy. The group agreed that further evidence for utility of FIT and urine VOC compared to colonoscopy was required hence very supportive of this study. Consequently, we have a Public Co-applicant who will contribute through overseeing of conduct and progress of the study from inception and design to delivery throughout the duration of RECEDE study. Specifically, the Public Co-applicant will review the PPI strategy throughout the project, support public dissemination of findings, writing of material that is appropriate for the target audience, co-author on manuscripts as well as being part of the TMG. Our Public Co-applicant also has first-hand experience of colonoscopies and will provide guidance in developing participant facing materials. He has been involved in developing other NIHR projects and has attended 'Being Part of a Research Team' workshop at Warwick CTU. Together with other PPI contributors, they will be funded to attend conferences as part of the research team and contribute to delivery of presentations to ensure participant/public perspective is included. Specific training needs will be identified and supported by UHCW (sponsor) accordingly.

#### 11.4 Data protection and participant confidentiality

The study will comply with the current Data Protection regulations and regular checks and monitoring will be undertaken by the Study Manger to ensure compliance. Participants will be assigned a unique identifier upon enrolment into the study to allow pseudonymisation of participant-identifiable data. Access to participant identifiable data will be restricted to members of the site study co-ordination team who require it for the performance of their role. Electronic data will be stored on password protected encrypted drives and hard copies of study documents will be stored in locked filing cabinets in secure entry-card protected sites.

#### **12 DISSEMINATION POLICY**

It is anticipated that broadly two important findings will emerge. From a clinical stand point, the utility of FIT plus urine VOC testing for SBD detection. This will enable us to determine if there is a group without SBD that can potentially avoid the need for a colonoscopy or CTC with quantification of potential cost savings. Naturally results will be of profound interest to clinicians worldwide that investigate lower gastrointestinal symptoms. Results can also be used by NICE to inform a revised pathway for managing participants with lower gastrointestinal symptoms – to categorise high risk i.e. those with SBD versus low risk (without SBD). Those with very low risk of SBD could potentially be managed in primary care without need to refer to secondary care.

This will lead to high level presentations at Gastrointestinal and Oncological meetings both nationally and internationally. It will also benefit from production of high quality open access manuscripts.

We will also evaluate the health economic impact as well as savings to the NHS which will be of interest to NICE. Hence results from RECEDE will form key evidence base for review of guidance on how to manage participants with lower gastrointestinal symptoms referred from primary care. Additionally, some co-applicants ([name]) have been involved in technology assessments by the NICE Diagnostics Programme, including the appraisal of faecal calprotectin. Care would be taken to produce the sort of evidence required by NICE, including costs per QALY.

A range of dissemination products to include annual reports, national publications, press releases through UHCW's Communications Department, participant safety collaborations, presentation and talks as well as videos will be included to ensure that all audiences can be updated. The team has close links with the West Midlands Academic Health Science Network (AHSN) and will make use of the Meridian Health Innovation Exchange Platform (https://meridian.wmahsn.org) to disseminate the results of the study. Through this, the wider national network of AHSN's will also be exploited for this purpose together with UHCW Communications and other online stakeholder case study platforms, including MidTECH and NHS Innovation Hub for the West Midlands region.

Finally, the disutility of colonoscopy and CTC will be evaluated in participants with symptoms – previous evaluation in 2010 was undertaken in those undergoing screening colonoscopies, but none in the larger group of those with symptoms referred for investigations.

Dissemination of results to participants will be led by our PPI co-applicant and facilitated through GUTs UK which is the partner charity of the British Society of Gastroenterology. We will also engage with key stakeholders including PPIE groups, local specialised colorectal Clinical Research Group (CRG), as well as Cancer Alliance groups.

All data arising from RECEDE will lie with the sponsor. Authorship in the final report will be granted (order to be agree) and in line with ICMJE guidance; http://www.icmje.org/recommendations/browse/roles-and-responsibilities/defining-the-role-of-authors-and-contributors.html for those that contributed directly to the study.

#### **13 APPENDICES** Appendix A Volatile compounds in urine

Appendix A Table 1 Summary of key VOCs identified in urine in those with SBD. Note that individually these compounds are non-discriminatory but collectively in their specific relative abundance these chemicals are discriminatory in the diagnosis of SBD.

VOLATILE COMPOUNDS (33,55,56)	DESCRIPTION
Acetone	Acetone has been shown to contribute to pH regulation within the mammals. It also has the potential to be used as a cellular fuel source to aid metabolic processes in the liver. It is produced by the oxidation of fatty acids by gut bacteria(57-59).
2-Pentanone	Common urinary volatile metabolite noted in different diseases. Also found in some foods (yoghurt, honey) with higher levels found in faeces (60).
4-Heptanone	4-heptanone is found in healthy control groups compared to leukaemia, CRC and lymphoma(61, 62).
1,3,5,7-Cyclooctatetraene	This chemical has not been noted in studies investigating the products of metabolic processes. It is linked with fermented wheat germ and provides a potential connection with the metabolic products being absorbed in the gut. We have noted its presence in coeliac disease and filed a patent (34).
Allyl Isothiocyanate	This chemical has been found to inhibit the growth of many strains of pathogenic intestinal bacteria associated with inflammation(63, 64).
Oxime-, methoxy-phenyl-	Production linked with Myxobacteria such as Sorangium cellulosum (64)
1,3-Propanediamine	Common metabolic molecule produced by certain bacteria. Also noted in the human gut(65, 66).
Carvone	Carvone is a food additive and natural product in mint and can inhibit the growth of fungal and bacterial microbes. It also inhibits quorum sensing which bacteria use to aid virulence(67).
Ethanone, 1,1'-(1,4- phenylene)bis	This compound has been linked to interactions between gut bacteria metabolism and host physiology in response to disease(68, 69).
Phenol, 2,4-bis(1,1- dimethylethyl)-	Common urinary volatile metabolite noted in health and disease. It is also thought to inhibit quorum sensing utilised by bacteria(70).

